6.3.4. Blood Donation

Subjects are required to refrain from donation of blood from 3 months prior to screening, plasma from 2 weeks prior to screening, and platelets from 6 weeks prior to screening until 3 months after the follow-up visit.

7. STUDY ASSESSMENTS AND PROCEDURES

Every effort will be made to schedule and perform the procedures as closely as possible to the nominal time, giving considerations to appropriate posture conditions, practical restrictions, and the other procedures to be performed at the same time point.

The highest priority procedures will be performed closest to the nominal time. The order of priority for scheduling procedures around a time point is (in descending order of priority):

- dosing
- blood samples for PK and exploratory metabolite profiling
- any other procedures (safety ECGs will be scheduled before vital signs measurements [except body temperature]; vital signs measurements [except body temperature] will be scheduled before blood sampling)

7.1. Pharmacokinetic Assessments

7.1.1. Pharmacokinetic Sample Collection and Processing

Blood samples (approximately 1 × 2-mL sample per scheduled time) for PK analysis of CCI [REDACTED] and blood samples (approximately 1 × 2-mL sample per scheduled time) for PK analysis of itraconazole and its metabolite hydroxy-itraconazole will be collected by venepuncture or cannulation at the times indicated in the Schedule of Assessments in Appendix 6. Furthermore, up to 3 additional blood samples may be taken from each subject per treatment period in Part A, and up to 6 additional blood samples may be taken from each subject in Parts B and C, with the maximum volume of blood withdrawn per subject will not exceed the limit detailed in Appendix 3. Any changes to the scheduled times of PK assessments will be agreed with the Sponsor and documented in the TMF. Blood samples taken from subjects who received placebo will not be analysed.

Procedures for collection, processing, and shipping of PK blood samples will be detailed in a separate document.

7.1.2. Pharmacokinetic Analytical Methodology

Plasma concentrations of CCI [REDACTED], itraconazole, and hydroxy-itraconazole will be determined using validated analytical procedures. Specifics of the analytical methods will be provided in separate documents.

7.2. Exploratory Assessments

7.2.1. Sample Collection and Processing for Exploratory Metabolite Profiling

For subjects in Groups A2a, A5, B1, and C1, blood samples (approximately 1×2 mL sample per scheduled time) will be collected by venepuncture or cannulation at the times indicated in the Schedule of Assessments in [Appendix 6](#). The maximum volume of blood withdrawn per subject will not exceed the limit detailed in [Appendix 3](#). Any changes to the scheduled times of blood sampling for metabolite profiling will be agreed with the Sponsor and documented in the TMF. Blood samples taken from subjects who received placebo will not be measured.

For subjects in Groups A2a and A5, predose spot urine and faecal samples and 24-hour urine and faecal samples will be collected into pre-weighed polyethylene containers over the time intervals indicated in the Schedule of Assessments in [Appendix 6](#). Faecal samples will be collected, as far as possible. For subjects in Groups B1, predose spot urine and 24-hour urine samples will be collected into pre-weighed polyethylene containers over the time intervals indicated in the Schedule of Assessments in [Appendix 6](#). Urine and faecal samples taken from subjects who received placebo will not be measured.

Procedures for collection, processing, and shipping of blood, urine, and faecal samples for metabolite profiling will be detailed in a separate document.

7.2.2. Methodology for Exploratory Metabolite Profiling Analysis

The analytical methods for exploratory metabolite profiling analysis may be provided in a separate document and will not form part of the Clinical Study Report for this study.

7.2.3. Sample Collection and Processing for Pharmacogenetic Analysis

Blood samples (approximately 1×10 -mL sample) will be collected by venepuncture or cannulation at the times indicated in the Schedule of Assessments in [Appendix 6](#). The maximum volume of blood withdrawn per subject will not exceed the limit detailed in [Appendix 3](#).

Subjects will only be required to provide a single sample for pharmacogenetic analysis during the course of the study. In the case that a pharmacogenetic sample is collected whilst a subject is standby for the sentinel group but is not then dosed as a sentinel a second pharmacogenetic sample is not required if that subject is subsequently enrolled in the main group.

7.2.4. Methodology for Pharmacogenetic Analysis

If pharmacogenetic analysis is undertaken, the analytical methods may be provided in a separate document and will not form part of the Clinical Study Report for this study.

7.2.5. Sample Collection and Processing for Exploratory Biomarker Analysis

Exploratory biomarker analysis in blood and urine will be performed on residual samples of exploratory metabolite profiling in Parts A and B.

7.2.6. Sample Collection and Processing for Analysis of Phospholipid-C and Faecal Calprotectin

Exploratory analysis of phospholipid-C in serum and faecal calprotectin will be performed on blood samples taken for safety clinical laboratory assessments and residual samples taken for faecal occult blood tests, respectively. Faecal calprotectin measurements will only be performed during the respective treatment period.

7.2.7. Methodology for Exploratory Biomarker Analysis

If exploratory biomarker analysis is undertaken, the analytical methods may be provided in a separate document and will not form part of the Clinical Study Report for this study.

7.2.8. Continuous 12-lead Electrocardiogram Monitoring

Continuous 12-lead ECG monitoring using a digital recorder will take place at the times indicated in the Schedule of Assessments in [Appendix 6](#). Continuous 12-lead ECG monitoring may be added to Part B; if added, the details will be documented and filed in the eTMF.

All continuous 12-lead ECG data collected will be archived without extraction or analysis and will not be reported in the scope of this study.

Environmental distractions (eg, television, radio, conversation) should be avoided during ECG recording, where possible.

7.3. Safety and Tolerability Assessments

7.3.1. Adverse Events

Adverse event definitions, assignment of severity and causality, and procedures for reporting SAEs are detailed in [Appendix 1](#).

The condition of each subject will be monitored from the time of signing the ICF to final discharge from the study. Subjects will be observed for any signs or symptoms and asked about their condition by open questioning, such as ‘how have you been feeling since you were last asked?’, at least once each day while resident at the study site and at each study visit. Subjects will also be encouraged to spontaneously report AEs occurring at any other time during the study.

Any AEs and remedial action required will be recorded in the subject’s source data. The nature, time of onset, duration, and severity will be documented, together with an Investigator’s (or designee’s) opinion of the relationship to study treatment.

Adverse events recorded during the course of the study will be followed up, where possible, until resolution or until the unresolved AEs are judged by the Investigator (or designee) to have stabilised. This will be completed at the Investigator’s (or designee’s) discretion.

7.3.2. Clinical Laboratory Evaluations

Clinical laboratory evaluations are listed in [Appendix 2](#). Total blood sampling volumes for an individual subject is shown [Appendix 3](#).

Blood, urine and faecal samples will be collected for clinical laboratory evaluations (including clinical chemistry, haematology, urinalysis, coagulation, and faecal occult blood test) at the times indicated in the Schedule of Assessments in [Appendix 6](#). Blood samples for clinical laboratory evaluations will be collected after at least 6-hour fast. Faecal samples in treatment periods will be collected as far as possible. If the latest result during the treatment period is positive, faecal samples will be collected for faecal occult blood test at the follow-up visit, as far as possible. If subjects collect faecal samples at home, the sample within 24 hours before the designated time point is acceptable. For female subjects, faecal samples at screening and the follow-up visit should be collected at least 3 days after the completion of menstruation.

Additional clinical laboratory evaluations will be performed at other times if judged to be clinically appropriate or if the ongoing review of the data suggests a more detailed assessment of clinical laboratory safety evaluations is required.

Subjects will be asked to provide urine samples for drugs of abuse screen and cotinine test, and will undergo an alcohol breath test at the times indicated in the Schedule of Assessments in [Appendix 6](#).

For all female subjects, serum and/or urine pregnancy tests and follicle-stimulating hormone test will be performed at the times indicated in the Schedule of Assessments in [Appendix 6](#), as applicable.

An Investigator (or designee) will perform a clinical assessment of all clinical laboratory data.

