Overall, 48 subjects will be studied in 5 groups (Groups A1 to A5); Groups A1, and A3 to A5 will consist of 8 male subjects, and Group A2 will consist of 16 subjects split into 2 subgroups (Group A2a [male subjects only] and Group A2b [female subjects only]) that will consist of 8 subjects each.

Potential subjects will be screened to assess their eligibility to enter the study within 28 days prior to the first dose administration. Each subject will participate in 1 treatment period only, except for Group A2a, where each subject will participate in 2 treatment periods where doses of KRP-A218 will be separated by an interval of 7 to 10 days (up to and including Day -1 of Treatment Period 2). The washout period may be extended depending on the observed apparent terminal elimination half-life ($t_{1/2}$) of CCI [REDACTED]. Subjects will reside at the study site from Day -1 (the day before dosing) to Day 4 of each treatment period.

All subjects will return for a follow-up visit 7 to 10 days after their final dose. The follow-up period may be extended depending on the observed $t_{1/2}$ of CCI [REDACTED]. In each of Groups A1, A2a, A2b, and A3 to A5, 6 subjects will receive KRP-A218 and 2 subjects will receive placebo. In Groups A1, A2b, and A3 to A5, all doses will be administered in the fasted state on the morning of Day 1. For Group A2a, Period 1, Day 1 doses will be administered in the fasted state and Period 2, Day 1 doses will be given 30 minutes after starting a standard high-fat breakfast. Each subject in Groups A1, A2b, and A3 to A5 will receive only a single dose of KRP-A218 or placebo during the study. In Group A2a, subjects will have the same treatment in both periods, such that each subject will receive 2 single doses of KRP-A218 or placebo during the study.

All groups in Part A (with the exception of Group A2a in Treatment Period 2) will receive the investigational medicinal product (IMP) using a sentinel approach. For each group, 2 subjects (1 KRP-A218 and 1 placebo) will receive the IMP at least 24 hours before the remaining subjects.

Part B:

There will be 4 groups, consisting of male subjects. Part B may overlap with Part A.

Overall, 40 subjects will be studied in 4 groups (Groups B1 to B4), with each group consisting of 10 male subjects. Part B may start after completion of Group A3, at dose equal to or less than given in Groups A1 to A3.

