11. History of alcoholism or drug/chemical abuse within 2 years prior to Day -1.
12. Alcohol consumption of >14 units per week. One unit of alcohol equals 1/2 pint (285 mL) beer or lager, 1 glass (125 mL) of wine, or 1/6 gill (25 mL) of spirits.
13. Positive alcohol breath test result or positive urine drug and cotinine screen (confirmed by repeat) at Screening or Day -1.
14. Positive hepatitis panel and/or positive human immunodeficiency virus test.
15. Positive faecal occult blood test. For female subjects, the faecal occult blood test should be conducted at least 3 days after the completion of menstruation.
16. Participation in a clinical study involving administration of an investigational drug (new chemical entity) in the past 90 days prior to dosing.
17. Use or intend to use any medications/products known to alter drug absorption, metabolism, or elimination processes, including St. John's wort, within 30 days prior to dosing.
18. Use or intend to use any prescription medications/products within 14 days or 5 half-lives (whichever is longer) prior to dosing, unless deemed acceptable by the Investigator (or designee).
19. Use or intend to use strong or moderate CYP3A4 inhibitors or inducers within 14 days or 5 half-lives (whichever is longer) prior to dosing.
20. Use or intend to use strong CYP2C9, 2C8 and 2D6 inhibitors or inducers within 14 days or 5 half-lives (whichever is longer) prior to dosing.
21. Use or intend to use slow release medications/products considered to still be active within 14 days prior to dosing, unless deemed acceptable by the Investigator (or designee).
22. Use or intend to use any nonprescription medications/products including vitamins, minerals, and phytotherapeutic/herbal/plant derived preparations within 7 days prior to dosing, unless deemed acceptable by the Investigator (or designee).
23. Use of tobacco or nicotine-containing products within 3 months prior to Day -1, or positive cotinine test at screening or Day -1.
24. Ingestion of poppy seed-, Seville orange-, or grapefruit-containing foods or beverages within 7 days prior to Day -1.
25. Consumption of caffeine- or xanthine-containing foods and beverages within 36 hours prior to Day -1.

26. Participation in strenuous exercise within 7 days prior to Day -1.
27. Receipt of blood products within 2 months prior to Day -1.
28. Donation of blood from 3 months prior to screening, plasma from 2 weeks prior to screening, or platelets from 6 weeks prior to screening.

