^a Interim medical history.^b Female subjects only.^c Female subjects only. Serum pregnancy test at screening and urine pregnancy test at all other timepoints. A positive urine pregnancy test will be confirmed with a serum pregnancy test.^d Subjects will be fasted for at least 10 hours prior to dosing until 4 hours after dosing, after which time a meal will be provided.^e Collected in Group A5 only.^f Spot urine and faecal samples will be collected any time prior to dosing in the treatment period. 24-hour urine and faecal samples will be collected on 0 to 24, 24 to 48, and 48 to 72 hours postdose. Faecal samples will be collected, as far as possible.^g A continuous 12-lead ECG will be obtained from 2 hours predose to 24 hours postdose. The 15-minute predose posture restriction (supinely or semi-recumbently resting in an undisturbed environment) for continuous ECG monitoring will be performed in triplicate within the first 2 hours prior to dosing. Postdose 15-minute posture restrictions for continuous ECG monitoring will be performed at 0.5, 0.75, 1, 1.5, 2, 3, 4, 6, 8, 12 and 24 hours postdose. Additional posture restrictions may be performed if deemed necessary after the review of PK data at the dose escalation review meetings.^h From waking-up to before breakfast.ⁱ Subjects will be fasted at least 6 hours before collection.^j Faecal occult blood test will be performed once each during the following sampling periods: Screening, Day -1 to prior to dosing, 0 to 24, 24 to 48, and 48 to 72 hours postdose. On screening, faecal samples will be collected to confirm eligibility for enrollment. For the other sampling periods, faecal samples will be collected as far as possible.^k If the latest result during the treatment period is positive, faecal samples will be collected for faecal occult blood test at the follow-up visit (within -2 day), as far as possible.^l To be assessed when collecting faecal samples for faecal occult blood test during the treatment period.^m Subjects should be supine for at least 5 minutes before blood pressure and pulse rate measurements.ⁿ To be measured in triplicate at approximately 2-minute intervals.^o To be recorded after the subject has been supine and at rest for at least 5 minutes.

^p Full physical examination.

^q Symptom-directed physical examination.

^r Prior to discharge.

^s To be performed at approximately the same time as on Day 1.

^t The follow-up period may be extended depending on the observed $t_{1/2}$ of CCI

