8.7.5. Bristol Stool Chart and Faecal Occult Blood Test

All Bristol stool chart and faecal occult blood test data will be listed.

Summary tables by treatment for Parts A and B and by overall for Part C will be provided for all Bristol stool chart and faecal occult blood test data. Additionally, summary tables by treatment and timepoint for Parts A and B and by timepoint for Part C will be provided for all Bristol stool chart scale and faecal occult blood test data.

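### In-treatment faecal occult blood samples from the female group (A2b) carry no menstruation rule or flag, yet all results are tabulated by treatment against a mostly male placebo pool

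*Protocol*

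**What the plan says.** - **Where the menstrual rule applies.** Protocol 4.2, exclusion criterion 15, sets it for eligibility: "For female subjects, the faecal occult blood test should be conducted at least 3 days after the completion of menstruation". Protocol 7.3.2 repeats it for two visits: "For female subjects, faecal samples at screening and the follow-up visit should be collected at least 3 days after the completion of menstruation".
- **What applies during treatment.** Protocol 7.3.2 says only: "Faecal samples in treatment periods will be collected as far as possible". Footnote j to Table 9 in Appendix 6, which covers A2b, calls for one test in each of these periods: "Screening, Day -1 to prior to dosing, 0 to 24, 24 to 48, and 48 to 72 hours postdose". It sets no menstrual condition.
- **Repeat testing.** Protocol 7.3.2: "If the latest result during the treatment period is positive, faecal samples will be collected for faecal occult blood test at the follow-up visit". This repeat too depends on whether a sample can be obtained.
- **Status of the endpoint.** Faecal occult blood is among the primary safety endpoints for Parts A and B (Protocol 2.2.1).
- **Reporting.** Under SAP 8.7.5, summary tables by treatment "will be provided for all Bristol stool chart and faecal occult blood test data", with further tables by treatment and timepoint. No menstruation flag, exclusion or footnote is described. SAP Table 1 gives active women their own 3 mg fasted-female label and pools placebo over all groups whatever the sex.
- **Who can be enrolled.** Appendix 4 admits women of childbearing potential, for example after tubal ligation or with a vasectomised partner. Protocol 6.1 bars hormonal contraceptives. Sterile and postmenopausal women are also eligible, and their number is not fixed.

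**The concern.** The protocol applies a safeguard where the test decides eligibility and where it checks recovery, but leaves it out of the samples taken to look for a drug effect. Nothing later in the plan separates the two possible sources of blood. The tables take every result, and SAP 8.1 and 8.7.6 do not list medical history, so menstrual information held there would not reach the reader.

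Gastrointestinal toxicity in dogs is the reason Protocol 3.5 gives for smaller escalation steps, so a positive in this test will draw attention. A2b is the only female group. A menstrual positive there would appear in a column made up wholly of women and be compared with a column of mostly men. With six active women, one such positive reads as 1 of 6 (17%).

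**Working it through.** The documents give no false-positive rate for this test and no sample size calculation, so there is no stated figure to reproduce. The check has two parts.

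**1. Does pooled placebo balance the contaminant?**

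Protocol synopsis: "In each of Groups A1, A2a, A2b, and A3 to A5, 6 subjects will receive KRP-A218 and 2 subjects will receive placebo".

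- Placebo in Part A: 6 groups or subgroups × 2 = 12, of whom 2 (those in A2b) are women and 10 are men.
- Women in the fasted-female active column: 6 of 6. Women in the pooled placebo column: 2 of 12 (17%).

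Pooling does not balance it.

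**2. How often could a postdose window coincide with menses?**

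Inputs from the documents: 3 postdose days (0 to 24, 24 to 48 and 48 to 72 h), the 3-day margin, and 6 active women. Assumptions that are not in the documents: a 28-day cycle, cycle phase random relative to dosing, 5 days of menses (range 3 to 7), and a share f of the women who menstruate.

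An interval of z days overlaps a 3-day span with probability (z + 3)/28.

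| Interval | Per menstruating woman | Expected of 6, f = 1 | Expected of 6, f = 0.5 | f = 0 |
|---|---|---|---|---|
| Menses only, z = 5 | (5 + 3)/28 = 29% | 1.7 | 0.9 | 0 |
| Menses plus margin, z = 8 | (8 + 3)/28 = 39% | 2.4 | 1.2 | 0 |

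The chance that at least one of the six overlaps is 1 − (1 − p)^6, where p = f × (z + 3)/28:

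- f = 1: 87% (z = 5) and 95% (z = 8).
- f = 0.5: 60% and 73%.

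Varying menses alone from 3 to 7 days moves the per-woman figure from (3 + 3)/28 = 21% to (7 + 3)/28 = 36%.

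On the same assumptions with f = 1, the expected overlap in the pooled placebo column is 2 × 0.286/12 = 4.8% to 2 × 0.393/12 = 6.5%, against 29% to 39% in the fasted-female column.

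All of these are chances that the timing coincides. How often a sample taken then would test positive is not known from the documents, and not every window will yield a sample. The figures are therefore upper bounds on menstrual false positives.

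**The case against.** **The table attributes nothing.** A reader might infer that a menstrual positive would be reported as a gastrointestinal effect of KRP-A218. The documents do not support that. SAP 8.7.5 plans descriptive counts, SAP 8.7.7 plans no inferential safety analysis, the formal sex comparison in SAP 8.5.3.3 concerns pharmacokinetics only, and the column is labelled female. Two of the eight women are on placebo, so their positives fall in the placebo column. This objection stands and limits the point to reporting.

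**Escalation is protected.** The bleeding criterion in Protocol 3.7 needs visible blood judged to be gastrointestinal, and an occult positive alone does not meet it. This also stands.

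**Not every unprotected window measures drug effect.** The Day -1 sample precedes dosing, so only three windows are postdose. The by-timepoint table shows the predose result separately and can reveal blood already present. That helps, but menses may start after dosing, and the predose sample is itself unprotected.

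**There are other safeguards.** The investigator assesses all laboratory data, and a positive last result leads to a follow-up sample that is covered by the menstrual rule. These make misreading less likely, but neither takes a positive out of the table. An early positive followed by a negative is not rechecked under this rule. A negative follow-up sample cannot tell menstruation from a transient drug effect.

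**The gap may be closed elsewhere.** The eCRF and table shells are separate documents and might capture menses dates or footnote the tables. That cannot be settled from the protocol and SAP.

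**Conclusion.** The gap is real and minor. The plan recognises a contaminant, protects two visits from it, and leaves unprotected and unflagged the in-treatment samples that feed a primary safety endpoint. Followed as written, it counts any menstrual positive in an active woman in the 3 mg fasted-female column, beside placebo that is 10 of 12 male.

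The size is at most about 1.7 to 2.4 of 6 active women with a postdose window in the affected period if all menstruate, half that if half do, and none if none do. This rests on the assumed 28-day cycle, random timing and 5 days of menses, and on the unknown share of menstruating women. It would be wrong to read 29% or 39% as a false-positive rate. The scope is one group of eight women and a descriptive table; escalation criteria and inferential analyses are unaffected.

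**What to change.** **Data.** Record the first and last day of menses for each woman in Group A2b. Protocol 1.3 reports 4 of the 8 already dosed at 27 August 2021; collect their dates retrospectively where possible, and show menstrual status as unknown where it is not.

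**SAP 8.7.5.** Add text to this effect: *Each Group A2b faecal occult blood sample, predose included, taken from the onset of menses to 3 days after its end will be flagged in the listing. All results stay in the main table. An added row or footnote will give positive and negative counts with flagged samples shown separately.*

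Flagged samples should not be dropped from the main counts. Removing them could hide a true bleed that happened to coincide with menses, on a primary safety endpoint in a first-in-human study.

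**Cost.** Menses dates as an extra data item and one extra table row or footnote, for at most 8 women, with possibly incomplete dates for those already dosed. No dosing, sampling time or clinical rule changes.
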